12.2. Appendix 2: Immune-related Diseases

Table 19 List of Potential Immune-mediated Diseases

Neuroinflammatory disorders	Musculoskeletal disorders	Skin disorders

 • Cranial nerve disorders, including paralyses/paresis (e.g. Bell's palsy) • Optic neuritis • Multiple sclerosis • Transverse myelitis • Guillain-Barré syndrome, including Miller Fisher syndrome and other variants • Acute disseminated encephalomyelitis, including site specific variants: e.g. non-infectious encephalitis, encephalomyelitis, myelitis, myeloradiculoneuritis • Myasthenia gravis, including Lambert-Eaton myasthenic syndrome • Immune-mediated peripheral neuropathies and plexopathies, (including chronic inflammatory demyelinating polyneuropathy, multifocal motor neuropathy and polyneuropathies associated with monoclonal gammopathy). • Narcolepsy 	
 • Systemic lupus erythematosus and associated conditions • Systemic Scleroderma (Systemic sclerosis), including diffuse systemic form and CREST syndrome • Idiopathic inflammatory myopathies, including Dermatomyositis, Polymyositis, • Antisynthetase syndrome • Rheumatoid arthritis and associated conditions including Juvenile chronic arthritis and Still's disease) • Polymyalgia rheumatica • Spondyloarthritis, including ankylosing spondylitis, reactive arthritis (Reiter's Syndrome) and undifferentiated spondyloarthritis • Psoriatic arthropathy • Relapsing polychondritis • Mixed connective tissue disorder 	
 • Psoriasis • Vitiligo • Erythema nodosum • Autoimmune bullous skin diseases (including pemphigus, pemphigoid and dermatitis herpetiformis) • Alopecia areata • Lichen planus • Sweet's syndrome • Localized Scleroderma (Morphoea)
Liver disorders	Gastrointestinal disorders	Endocrine disorders

 • Autoimmune hepatitis • Primary biliary cirrhosis • Primary sclerosing cholangitis • Autoimmune cholangitis. 	
 • Inflammatory Bowel disease, including Crohn's disease, ulcerative colitis, microscopic colitis, ulcerative proctitis • Celiac disease • Autoimmune pancreatitis 	
 • Autoimmune thyroiditis (including Hashimoto thyroiditis) • Grave's or Basedow's disease • Diabetes mellitus type I • Addison's disease • Polyglandular autoimmune syndrome • Autoimmune hypophysitis

Vasculitides	Blood disorders	Others

 • Large vessels vasculitis including: giant cell arteritis such as Takayasu's arteritis and temporal arteritis. • Medium sized and/or small vessels vasculitis including: polyarteritis nodosa, Kawasaki's disease, microscopic polyangiitis, Wegener's granulomatosis, Churg–Strauss syndrome (allergic granulomatous angiitis), Buerger's disease (thromboangiitis obliterans), necrotizing vasculitis and anti-neutrophil cytoplasmic antibody (ANCA) positive vasculitis (type unspecified), Henoch-Schonlein purpura, Behcet's syndrome, leukocytoclastic vasculitis. 	
 • Autoimmune hemolytic anemia • Autoimmune thrombocytopenia • Antiphospholipid syndrome • Pernicious anemia • Autoimmune aplastic anemia • Autoimmune neutropenia • Autoimmune pancytopenia 	
 • Autoimmune glomerulonephritis (including IgA nephropathy, glomerulonephritis rapidly progressive, membranous glomerulonephritis, membranoproliferative glomerulonephritis, and mesangioproliferative glomerulonephritis) • Ocular autoimmune diseases (including autoimmune uveitis and autoimmune retinopathy) • Autoimmune myocarditis/cardiomyopathy • Sarcoidosis • Stevens-Johnson syndrome • Sjögren's syndrome • Idiopathic pulmonary fibrosis • Goodpasture syndrome • Raynaud's phenomenon

12.3. Appendix 3: Liver Safety – Study Treatment Restart or Rechallenge Guidelines

If subject meets liver chemistry stopping criteria do not restart/rechallenge subject with study treatment unless:

- GSK Medical Governance approval **is granted** (as described below),
- Ethics and/or IRB approval is obtained, if required, and
- Separate consent for treatment restart/rechallenge is signed by the subject

If GSK Medical Governance approval to restart/rechallenge subject with study treatment **is not granted**, then subject must permanently discontinue study treatment and may continue in the study for protocol-specified follow-up assessments.

Rechallenge Following Liver Stopping Events that are Possibly Related to Study Treatment

Following drug-induced liver injury, **drug rechallenge is associated with 13% mortality across all drugs in prospective studies** [Andrade, 2009]. Clinical outcomes vary by drug, with nearly 50% fatality with halothane re-administered within one month of initial injury. However, some drugs seldom result in recurrent liver injury or fatality.

Risk factors for a fatal drug rechallenge outcome include:

- Hypersensitivity [Andrade, 2009] with initial liver injury (e.g. fever, rash, eosinophilia)
- jaundice or bilirubin >2xULN with initial liver injury (direct bilirubin >35% of total)
- subject currently exhibits severe liver injury defined by: ALT \geq 3xULN, bilirubin \geq 2xULN (direct bilirubin >35% of total), or INR \geq 1.5
- SAE or fatality has earlier been observed with drug rechallenges [Papay, 2009; Hunt, 2010]
- evidence of drug-related nonclinical liability (e.g. reactive metabolites; mitochondrial impairment [Hunt, 2010])

Rechallenge refers to resuming study treatment following drug-induced liver injury (DILI). Because of the risks associated with rechallenge after DILI this should only be considered for a subject for whom there is compelling evidence of benefit from a critical or life-saving medicine, there is no alternative approved medicine available, and a benefit:risk assessment of rechallenge is considered to be favorable.

Approval by GSK for rechallenge with study treatment can be considered where:

- Investigator requests consideration of rechallenge with study treatment for a subject who is receiving compelling benefit with study treatment that exceeds risk, and no effective alternative therapy is available.

- Ethics Committee or IRB approval for rechallenge with study treatment must be obtained, as required.
- If the rechallenge is approved by GSK Medical Governance in writing, the subject must be provided with a clear description of the possible benefits and risks of study treatment administration, including the possibility of recurrent, more severe liver injury or death.
- The subject must also provide signed informed consent specifically for the rechallenge with study treatment. Documentation of informed consent must be recorded in the study chart.
- Study treatment must be administered at the dose specified by GSK.
- Subjects approved by GSK Medical Governance for rechallenge with study treatment must return to the clinic twice a week for liver chemistry tests until stable liver chemistries have been demonstrated and then standard laboratory monitoring may resume as per protocol.
- If after study treatment rechallenge, subject meets protocol-defined liver chemistry stopping criteria, study treatment should be permanently discontinued.
- GSK Medical Monitor, and the Ethics Committee or IRB as required, must be informed of the subject's outcome following study treatment rechallenge.
- GSK to be notified of any AEs, as per Section 7.4.1.

AND/OR

Restart Following Transient Resolving Liver Stopping Events NOT Related to Study Treatment

Restart refers to resuming study treatment following liver stopping events in which there is a clear underlying cause (other than DILI) of the liver event (e.g., biliary obstruction, pancreatic events, hypotension, acute viral hepatitis). Furthermore, there should be no evidence of alcoholic hepatitis or hypersensitivity, and the study treatment should not be associated with HLA markers of liver injury.

Approval by GSK for study treatment restart can be considered where:

- Investigator requests consideration for study treatment restart if liver chemistries have a clear underlying cause (e.g., biliary obstruction, hypotension and liver chemistries have improved to normal or are within 1.5 x baseline and ALT <3xULN).
- Restart risk factors (e.g., fever, rash, eosinophilia, or hypersensitivity, alcoholic hepatitis, possible study treatment-induced liver injury or study treatment has a human leukocyte antigen (HLA) genetic marker associated with liver injury (e.g., lapatinib, abacavir, amoxicillin/clavulanate) are reviewed and excluded.
- Ethics Committee or IRB approval of study treatment restart must be obtained, as required.

- If restart of study treatment is approved by GSK Medical Governance in writing, the subject must be provided with a clear description of the possible benefits and risks of study treatment administration, including the possibility of recurrent, more severe liver injury or death.
- The subject must also provide signed informed consent specifically for the study treatment restart. Documentation of informed consent must be recorded in the study chart.
- Study treatment must be administered at the dose specified by GSK.
- Subjects approved by GSK Medical Governance for restarting study treatment must return to the clinic once a week for liver chemistry tests until stable liver chemistries have been demonstrated and then laboratory monitoring may resume as per protocol.
- If after study treatment re-start, subject meets protocol-defined liver chemistry stopping criteria, follow usual stopping criteria instructions.
- GSK Medical Monitor, and the Ethics Committee or IRB as required, must be informed of the subject's outcome following study treatment restart.
- GSK to be notified of any AEs, as per Section [7.4.1](#).

12.4. Appendix 4: NYHA Functional Classification System for Heart Failure

The New York Heart Association (NYHA) Functional Classification [[NYHA, 1994](#)] provides a simple way of classifying the extent of heart failure. It places subjects in one of four categories based on the level of limitation experienced during physical activity:

Class	Symptoms
Class I (Mild)	No limitation of physical activity. Ordinary physical activity does not cause undue fatigue, palpitation or dyspnea (shortness of breath).
Class II (Mild)	Slight limitation of physical activity. Comfortable at rest, but ordinary physical activity results in fatigue, palpitation or dyspnea.
Class III (Moderate)	Marked limitation of physical activity. Comfortable at rest, but less than ordinary physical activity results in fatigue, palpitation or dyspnea.
Class IV (Severe)	Unable to carry out any physical activity without discomfort. Symptoms of cardiac insufficiency at rest. If any physical activity is undertaken, discomfort is increased.

12.5. Appendix 5: Guidelines for Assessment of Disease, Disease Progression and Response Criteria – adapted from RECIST version 1.1

12.5.1. Assessment Guidelines

Please note the following:

- The same diagnostic method, including use of contrast when applicable, must be used throughout the study to evaluate a lesion. Contrast agents must be used in accordance with the Image Acquisition Guidelines.
- All measurements should be taken and recorded in millimeters (mm), using a ruler or calipers.
- Ultrasound is not a suitable modality of disease assessment. If new lesions are identified by ultrasound, confirmation by CT or MRI is required.
- Fluorodeoxyglucose (FDG)-PET is generally not suitable for ongoing assessments of disease. However FDG-PET can be useful in confirming new sites of disease where a positive FDG-PET scans correlates with the new site of disease present on CT/MRI or when a baseline FDG-PET was previously negative for the site of the new lesion. FDG-PET may also be used in lieu of a standard bone scan providing coverage allows interrogation of all likely sites of bone disease and FDG-PET is performed at all assessments.
- If PET/CT is performed then the CT component can only be used for standard response assessments if performed to diagnostic quality, which includes the required anatomical coverage and prescribed use of contrast. The method of assessment should be noted as CT on the eCRF.

Clinical Examination: Clinically detected lesions will only be considered measurable when they are superficial (e.g., skin nodules). In the case of skin lesions, documentation by color photography, including a ruler/calipers to measure the size of the lesion, is required.

CT and MRI: Contrast enhanced CT with 5mm contiguous slices is recommended.

Minimum size of a measurable baseline lesion should be twice the slice thickness, with a minimum lesion size of 10 mm when the slice thickness is 5 mm. MRI is acceptable, but when used, the technical specification of the scanning sequences should be optimized for the evaluation of the type and site of disease and lesions must be measured in the same anatomic plane by use of the same imaging examinations. Whenever possible, the same scanner should be used.

X-ray: In general, X-ray should not be used for target lesion measurements owing to poor lesion definition. Lesions on chest X-ray may be considered measurable if they are clearly defined and surrounded by aerated lung; however chest CT is preferred over chest X-ray.

Brain Scan: If brain scans are required, then contrast enhanced MRI is preferable to contrast enhanced CT.

12.5.2. Guidelines for Evaluation of Disease

12.5.2.1. Measurable and Non-measurable Definitions

12.5.2.1.1. Measurable lesion:

A non-nodal lesion that can be accurately measured in at least one dimension (longest dimension) of

- ≥ 10 mm with MRI or CT when the scan slice thickness is no greater than 5 mm. If the slice thickness is greater than 5 mm, the minimum size of a measurable lesion must be at least double the slice thickness (e.g., if the slice thickness is 10 mm, a measurable lesion must be ≥ 20 mm).
- ≥ 10 mm caliper/ruler measurement by clinical exam or medical photography.
- ≥ 20 mm by chest X-ray.
- Additionally lymph nodes can be considered pathologically enlarged and measurable if

≥ 15 mm in the short axis when assessed by CT or MRI (slice thickness recommended to be no more than 5 mm). At baseline and follow-up, only the short axis will be measured.

12.5.2.1.2. Non-measurable lesion:

All other lesions including lesions too small to be considered measurable (longest diameter < 10 mm or pathological lymph nodes with ≥ 10 mm and < 15 mm short axis) as well as truly non-measurable lesions, which include: leptomeningeal disease, ascites, pleural or pericardial effusions, inflammatory breast disease, lymphangitic involvement of the skin or lung, abdominal masses/abdominal organomegaly identified by physical exam that is not measurable by reproducible imaging techniques

Measurable disease: The presence of at least one measurable lesion. Palpable lesions that are not measurable by radiologic or photographic evaluations may not be utilized as the only measurable lesion.

Non-Measurable only disease: The presence of only non-measurable lesions. Note: non-measurable only disease is not allowed per protocol.

12.5.2.2. Immune-Related RECIST Response Criteria

12.5.2.2.1. Evaluation of target lesions

New, measurable ^a lesions	Incorporated into tumor burden
New, nonmeasurable lesions	Do not define progression (but preclude irCR)
irCR	Disappearance of all lesions in two consecutive observations not less than 4 weeks apart. Any pathological lymph nodes (whether target or non-target) must have reduction in short axis to <10 mm.
irPR	≥30% decrease in tumor burden compared with baseline in two observations at least 4 weeks apart
irSD	30% decrease in tumor burden compared with baseline cannot be established nor 20% increase compared with nadir
irPD ^b	At least 20% increase in tumor burden compared with nadir (at any single time point) in two consecutive observations at least 4 weeks apart. In addition to the relative increase of 20%, the sum must also demonstrate an absolute increase of at least 5 mm.

a. Measurable according to RECIST v1.1.

b. Treatment decisions will be based upon the immune-related RECIST criteria.

12.5.2.2.2. Antitumor response based on total measurable tumor burden

For the Modified RECIST criteria based on RECIST v1.1 and Immune-Related RECIST Criteria [Wolchok, 2009], the initial index and measurable new lesions are taken into account. At the baseline tumor assessment, the sum of the longest diameters (SLD) in the plane of measurement of all index lesions (maximum of five lesions total (and a maximum of two lesions per organ) representative of all involved) is calculated. Note: If lymph nodes are included in the SLD, only the short axis of the lymph node(s) is added into the sum. The short axis is the longest perpendicular diameter to the longest diameter of a lymph node or nodal mass. At each subsequent tumor assessment, the SLD of the baseline index lesions and of new, measurable lesions (≥10 mm; up to 5 new lesions per organ: 5 new cutaneous lesions and 10 visceral lesions) are added together to provide the total tumor burden:

$$\text{Tumor Burden} = \text{SLD}_{\text{index lesions}} + \text{SLD}_{\text{new, measurable lesions}}$$

12.5.2.2.3. Time-point response assessment using the Immune-Related RECIST criteria

Percentage changes in tumor burden per assessment time point describe the size and growth kinetics of both conventional and new, measurable lesions as they appear. At each tumor assessment, the response in index and new, measurable lesions is defined based on the change in tumor burden (after ruling out irPD). Decreases in tumor burden must be

assessed relative to baseline measurements (i.e., the SLD of all index lesions at screening).

12.5.2.2.4. Evaluation of non-target lesions

Definitions for assessment of response for non-target lesions are as follows:

- Complete Response (CR): The disappearance of all non-target lesions. All lymph nodes identified as a site of disease at baseline must be non-pathological (e.g. <10 mm short axis).
- Non-CR/Non-PD: The persistence of 1 or more non-target lesion(s) or lymph nodes identified as a site of disease at baseline ≥ 10 mm short axis.
- Progressive Disease (PD): Unequivocal progression of existing non-target lesions.
- Not Applicable (NA): No non-target lesions at baseline.
- Not Evaluable (NE): Cannot be classified by one of the four preceding definitions.

Note:

- In the presence of measurable disease, progression on the basis of solely non-target disease requires substantial worsening such that even in the presence of SD or PR in target disease, the overall tumor burden has increased sufficiently to merit discontinuation of therapy.
- Sites of non-target lesions, which are not assessed at a particular time point based on the assessment schedule, should be excluded from the response determination (e.g. non-target response does not have to be "Not Evaluable").

12.5.2.2.5. New lesions

New malignancies denoting disease progression must be unequivocal. Lesions identified in follow-up in an anatomical location not scanned at baseline are considered new lesions.

Any equivocal new lesions should continue to be followed. Treatment can continue at the discretion of the investigator until the next scheduled assessment. If at the next assessment the new lesion is considered to be unequivocal, progression should be documented.

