9.4.2. Secondary Analyses

9.4.2.1. Anticancer Activity Analyses

The All Treated Population will be used for anticancer activity analyses. Since this is a Phase I study, anticancer activity will be evaluated based on clinical evidence and response criteria. If data warrant, the response data will be summarized by dose level. irRECIST is the primary measure of clinical activity for response endpoints; RECIST v1.1 guidelines are used for disease measurements.

If the data warrant, ORR, DCR, TTR, and DOR will be calculated and listed for each subject.

ORR is defined as the percentage of subjects with a best overall confirmed CR or PR at any time as per disease-specific criteria (refer to [Appendix 5](#)). DCR is defined as the percentage of subjects with a confirmed CR + PR at any time, plus SD ≥ 12 weeks.

DOR will be calculated and listed for subjects with a confirmed CR or PR and is defined as the first documented evidence of CR or PR until disease progression or death due to any cause among subjects who achieve an overall response (i.e., unconfirmed or confirmed CR or PR). TTR is defined as the interval from the first dose of study treatment to the date of the first documented CR or PR. DOR and TTR are considered as exploratory endpoints. No summary tables for DOR and TTR will be provided.

Further details will be provided in the RAP.

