12.5.3. Evaluation of overall response

[Table 20](#) presents the overall response at an individual time point for all possible combinations of tumor responses in target and non-target lesions with or without the appearance of new lesions for subjects with measurable disease at baseline.

Table 20 Evaluation of Overall Response for Subjects with Measurable Disease at Baseline

Target Lesions	Non-Target Lesions	New Lesions	Overall Response
CR	CR or NA	No	CR
CR	Non-CR/Non-PD or NE	No	PR
PR	Non-PD or NA or NE	No	PR
SD	Non-PD or NA or NE	No	SD
NE	Non-PD or NA or NE	No	NE
PD	Any	Yes or No	PD
Any	PD	Yes or No	PD
Any	Any	Yes	PD

CR = Complete response, PR = Partial response, SD = Stable disease, PD = Progressive disease, NA = Not applicable, and NE = Not Evaluable

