## 12.2. Summary Measure

The evaluation of anticancer activity will be evaluated based on the All Treated Population as defined in [Section 7](#) unless otherwise specified. Since this is a Phase I study, anticancer activity will be evaluated based on clinical evidence and response criteria. If data warrant, the response data will be summarized by dose level or expansion cohort type.

Lesion assessment method and timing, evaluation of disease, disease progression and response criteria will be conducted according to RECIST (version 1.1) [[Eisenhauer, 2009](#)] and irRECIST as outlined in Appendix 5 of the protocol. irRECIST will be used to determine treatment decisions and will be used for the primary analysis of anticancer activity.

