### 12.2.1.1.2. Confirmed Best Overall Response per irRECIST Criteria

Besides the principles specified in [Section 12.2.1.1.1](#), the below principle needs to be considered when deriving the confirmed BOR per irRECIST.

- To be assigned a status of confirmed irPD, a confirmatory disease assessment should be performed at the next disease assessment no less than 4 weeks (28 days) after the criteria for irPD are first met.
- irPD will not override a subsequent best overall response of irSD, irPR, or irCR, meaning that irPR or irSD can be assigned (timepoint response or BOR) even if new lesions have not regressed, or if unequivocal progression (non-target lesions) remains unchanged, providing that the criteria for confirmation of irPD are not met.

Confirmed and confirmed BOR per irRECIST (irBOR) takes into account the requirement for confirmation of irCR, irPR, and irPD. If irBOR is irPD and is confirmed consecutively, irBOR will be termed as irCPD.

If irBOR is irPD but not confirmed and there is no subsequent irSD, irPR, or irCR (e.g. NE or lost follow-up), the confirmed and unconfirmed irBOR will be termed as irUPD. If irBOR is irPD but not confirmed and there is no subsequent irSD, irPR, or irCR (e.g. NE or lost follow-up) due to study conclusion, the confirmed BOR will be termed as N/A (not applicable) and the unconfirmed irBOR will be termed as irUPD.

Examples of Scenarios of Assignments of Confirmed/Unconfirmed Best Overall Response Using irRECIST (assuming the adjacent timepoints are 28 days apart at least):

Case	Timepoint Response 1	Timepoint Response 2	Timepoint Response 3	Timepoint Response 4	Timepoint Response 5	Timepoint Response 6	Confirmed BOR	Unconfirmed BOR
1	irSD [1]	irPR	irPR	irCR	irCR	irPD	irCR	irCR
2	irPR	irSD [1]	irPR				irSD	irPR
3	irSD [2]	NE					NE	NE
4	irSD [2]	irCR	irCR	irPD			irCR	irCR
5	irSD	irSD	irSD	irPR			irSD	irPR
6	irPR	irPR	irPD	irPD			irPR	irPR
7	irPD	irPD [4]					irCPD	irCPD
8	irPD [3]	irPD [4]					N/A	irUPD
9	irPD	irSD [1]	irPD				irSD	irSD
10	irPD [4]						N/A	irUPD
11	irSD [2]	irPD [4]					N/A	irUPD
12	NE	irPD [4]					N/A	irUPD
13	irPD	NE	NE	NE	NE	NE	N/A	irUPD

Assume any two adjacent assessments are at least 28 days apart

- [1] Assessment at least 77 days after the first dose
- [2] Assessment less than 77 days after the first dose
- [3] This assessment and next assessment is < 28 days
- [4] Last assessment before the subject died/discontinued from study

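### The irRECIST section of the protocol holds two incompatible new-lesion rules, and the SAP does not say which one drives the response classification

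*Protocol*

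**What the plan says.** Protocol 9.4.2.1 sets the hierarchy: "irRECIST is the primary measure of clinical activity for response endpoints; RECIST v1.1 guidelines are used for disease measurements". SAP 12.2 takes its rules from "irRECIST as outlined in Appendix 5 of the protocol", so whatever Appendix 5 says about new lesions carries into the analysis.

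In Appendix 5, section 12.5.2.2 is headed as the irRECIST criteria. The table in 12.5.2.2.1 says that new measurable lesions are "Incorporated into tumor burden". Of new non-measurable lesions it says "Do not define progression (but preclude irCR"). Section 12.5.2.2.2 computes burden from "the SLD of the baseline index lesions and of new, measurable lesions", and 12.5.2.2.3 bases the time-point response on the change in that burden. irPD requires a rise from nadir of 20% or more, and of 5 mm or more, on two consecutive observations four weeks or more apart.

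Still under the irRECIST heading, 12.5.2.2.5 deals with equivocal new lesions that are being followed: "If at the next assessment the new lesion is considered to be unequivocal, progression should be documented". It sets no size or burden condition and makes no exception for non-measurable lesions.

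Section 12.5.3 follows. Its Table 20 "presents the overall response at an individual time point for all possible combinations of tumor responses in target and non-target lesions", and its last row makes any new lesion PD. The table does not say which criterion it serves.

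SAP 12.2.1.1.2 states that "irPR or irSD can be assigned (timepoint response or BOR) even if new lesions have not regressed", but only as long as irPD has not been confirmed. Best overall response is programmed from the investigator's call at each time point (Protocol 12.5.3.1; SAP 12.2.1.1).

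**The concern.** One set of lesion measurements should give one irRECIST category. Here an investigator who follows the burden rule and one who follows 12.5.2.2.5 can both claim to be applying irRECIST as the protocol defines it, and reach opposite answers. The SAP builds best overall response from those calls and does not specify re-deriving irRECIST response from the lesion measurements, so any difference passes straight through.

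Three outputs are exposed: ORR, where irPR competes with PD; DCR, where irSD also competes with PD; and the progression date in the DOR listing, which SAP 12.2.4.1 takes from the first irPD that is later confirmed.

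**Working it through.** The plan states no figure that depends on this rule, so there is nothing to reproduce. The check applies both rules to the same scans.

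Inputs from Protocol 12.5.2.2.1 and 12.5.2.2.2:
- Burden = index-lesion sum + sum of new measurable lesions.
- irPR: burden at or below 70% of baseline, seen twice at least 4 weeks apart.
- irPD: burden at least 120% of nadir and at least 5 mm above it, on two consecutive observations.

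Illustrative assumption: baseline index sum 100 mm, and nadir 100 mm at the first post-baseline scan. Change = (burden − 100)/100.

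| Index (mm) | New (mm) | Burden (mm) | Change | Burden rule | 12.5.2.2.5 |
|---|---|---|---|---|---|
| 50 | 12 | 62 | −38% | irPR | PD |
| 60 | 10 | 70 | −30% | irPR | PD |
| 60 | 12 | 72 | −28% | irSD | PD |
| 100 | 19 | 119 | +19% | irSD | PD |
| 100 | 20 | 120 | +20% | irPD threshold met | PD |

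In these examples the rules agree only once burden reaches +20%. For a non-measurable new lesion the clash needs no arithmetic: 12.5.2.2.1 says it does not define progression, while 12.5.2.2.5 has progression documented once it is unequivocal.

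Confirmation does not remove the difference. Take the first row and suppose the scan is unchanged at least 28 days later:
- Burden rule: burden is 62 mm and nadir is now 62 mm, so the change from nadir is 0% and from baseline −38%. The scan is irPR again, giving confirmed irPR.
- 12.5.2.2.5: the same unequivocal new lesion gives a second consecutive progression call. Under SAP 12.2.1.1.2 that can be read as confirmed irPD (irCPD).

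The SAP sentence on persisting new lesions does not decide between these, because its condition is that irPD has not been confirmed, and whether it has been is the point in dispute.

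Size per reclassified subject = 100/n points. Protocol 4.1.1 caps a dose level at 12 subjects: 100/12 = 8.3. Smaller groups move more: 100/9 = 11.1 and 100/5 = 20.0. These are effects per subject, not estimates of how many subjects are affected.

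**The case against.** The strongest reply is that 12.5.2.2.5 and Table 20 are RECIST v1.1 text that has ended up under or beside the irRECIST material.

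For Table 20 this is largely persuasive. It sits in 12.5.3, outside the irRECIST heading, and uses CR, PR, SD and PD without the ir prefix. It closely resembles the table in SAP 12.1, whose columns are all labelled RECIST v1.1 and which also makes any new lesion PD. Section 12.5.2.2.3 meanwhile gives irRECIST its own time-point rule. A reader might infer that Table 20 imposes PD under irRECIST; the documents do not go that far. The table is only unlabelled. A label is still needed, because Appendix 5 defines target-lesion response only in the irRECIST table, so the target column of Table 20 has no other source within the appendix.

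For 12.5.2.2.5 the reply may describe the intention, but the section number and heading say otherwise, and nothing in the text limits it to RECIST v1.1.

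A reader might also infer that the SAP takes the opposite position to 12.5.2.2.5. It does not. Its permission is conditional, and its wording is compatible with a new lesion prompting an initial irPD that later scans fail to confirm. The SAP leaves the question open.

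Two further objections stand. ORR and DCR are secondary endpoints with no treatment comparison. All subjects had completed treatment by 5 November 2019, and Amendment 4 ended the requirement for further disease assessments, so rewording the protocol cannot change calls already made. Nor do the documents show how sites applied the text: that the two criteria merged at some sites and not at others is a possibility, not a finding.

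**Conclusion.** Wrong as written. Within the primary response criterion, 12.5.2.2.1 to 12.5.2.2.3 and 12.5.2.2.5 give incompatible instructions on new lesions, and the SAP inherits the conflict without resolving it.

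The consequence is bounded but not quantified. One reclassified subject moves ORR or DCR by 8.3 points in a full 12-subject dose level, and by more in a smaller one. For ORR this requires a pair of scans, since response must be confirmed. A reader might apply 11.1 points to ORR in the nine-subject melanoma and sarcoma expansion cohorts; the documents do not support that as an expected effect, because no responses were observed in Part 2B. ORR exposure is therefore mainly in Parts 1A and 2A. A choice between irSD and PD can still move DCR in any cohort, including Part 2B.

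The conclusion rests on reading 12.5.2.2.5 where it stands, under the irRECIST heading. The lesion sizes above are illustrative. Because irRECIST also governs discontinuation for progression, no view is taken on which rule is right for treatment decisions.

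**What to change.** The sponsor should reconcile Protocol 12.5.2.2.1 to 12.5.2.2.3, 12.5.2.2.5 and Table 20 by stating which criterion each serves.

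For the analysis:
- State in SAP 12.1 and 12.2.1.1.2 the new-lesion rule used to derive irRECIST response, including whether a new lesion alone counts as irPD and whether its persistence counts as confirmation.
- Before database freeze, flag for query every irPD time point that rests only on a new lesion while total burden (index plus new measurable) is below the threshold of +20% and 5 mm from nadir.
- If any such time points exist, report ORR and DCR with them classified each way.

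The cost is one SAP clarification and one data check on lesion data already collected, assuming that the new-lesion measurements needed for 12.5.2.2.2 are in the database. No new assessments are needed. SAP section 1 places final-analysis decisions before freeze, so the timing fits.
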